**Comparative Effectiveness of Particulate Versus
Nonparticulate Corticosteroid Injections for the Treatment
of Musculoskeletal Conditions**

Study Protocol and Statistical Analysis Plan

NCT04278833

April 7, 2020

1) Name of study:

Comparative Effectiveness of Particulate versus Nonparticulate Steroid Injections for Treating Musculoskeletal Conditions

2) PI and other key investigators or key study personnel

PI: [name]

Investigator: [name]

Research coordinator: [name], CCRC

3) Specific source of institutional funding (account number): None**4) List of sources from whom you are seeking funds (or have sought funding) for this project**

AMSSM funding

Stanford internal funding

PM&R foundation

Charity from donors

5) Specific aims and basic hypothesis including an explicit primary hypothesis or goal**Specific Aims:**

- a. To determine if particulate or non-particulate corticosteroid injections are more effective at treating pain from musculoskeletal pathologies of the intra-articular hip, glenohumeral joint, biceps tendon, and subacromial bursa at 2 weeks, 3 months, or 6 months.
- b. To determine if there is a significantly different side effect profile between particulate and non-particulate corticosteroids when used for intra-articular hip, glenohumeral joint, biceps tendon, or subacromial bursa injections.

Hypothesis: There will be no significant difference in pain reduction, number of injections received, conversion to surgery, or side effect profile at 2 weeks, 3 months, or 6 months between particulate and non-particulate corticosteroids in the treatment of musculoskeletal pathologies of the intra-articular hip, glenohumeral joint, biceps tendon, or subacromial bursa.

6) General background

Corticosteroid injections are commonly used for the treatment of painful musculoskeletal pathologies including hip and glenohumeral joint osteoarthritis, adhesive capsulitis, biceps tendinopathy, and impingement syndrome/subacromial bursitis (Lambert et al, 2007; Lee et al, 1997; Yoon et al, 2013; Hong et al, 2011), yet there is no consensus on whether particulate or non-particulate steroids are superior. Particulate steroids include betamethasone, triamcinolone, and methylprednisolone, while non-particulate steroids include dexamethasone (Derby et al, 2008).

While particulate steroids might have theoretical improved efficacy due to possible decreased dispersion from the intra-articular space, there is animal data to suggest that particulate steroids may decrease microvascular perfusion (Laemell et al, 2016). Moreover, during animal studies in which steroids were directly injected into the arterial circulation, particulate but not non-particulate steroids resulted in permanent central nervous system damage (Dawdley et al, 2009; Okubadejo et al, 2008). Yet because there is no meaningful data to support one choice over another, there remains significant clinical equipoise.

This is in contrast to spinal epidural corticosteroid injections, where dexamethasone is generally preferred due to comparable efficacy and improved safety profile of non-particulate steroids compared to particulate steroids (Kennedy et al, 2014; Mehta et al, 2017).

While randomized controlled trials have been completed comparing particulate to non-particulate steroids in the treatment of spinal stenosis (Kennedy et al, 2014; Mehta et al, 2017), knee rheumatoid arthritis (Hajialilo et al, 2016), and idiopathic trigger finger (Ring et al, 2008) with conflicting results, there have been no studies comparing these two steroid types in the hip joint, glenohumeral joint, biceps tendon, or subacromial/subdeltoid bursa.

7) Preliminary unpublished data: None

8) Experimental design and data analysis, including inclusion and exclusion criteria, statistical basis for the number of subjects to be enrolled, the statistical plan for analyzing at least the primary hypothesis, matrix showing procedure plan for each study visit, data safety monitoring plan .

Design

This will be a single center, prospective, single blind, randomized controlled trial of hip, glenohumeral joint, peri-tendinous biceps brachii, and subacromial bursa injections comparing the efficacy of particulate (triamcinolone, betamethasone) versus non-particulate (dexamethasone) corticosteroids.

Participants will be recruited for the study by trained physicians and physician extenders at Stanford orthopedic and PM&R clinics only after they have already opted for corticosteroid injection as a part of their routine medical care. The initial decision to pursue steroid injection will be based entirely on joint decision making between the patient and their medical provider prior to mention of the study.

After consenting, basic demographic data, average numeric pain score (NRS) over the past week, and information on other medical interventions tried for their pain (including medication use, physical therapy, chiropractic care, and massage) will be collected. The participant will then be randomized to receive either a particulate (triamcinolone or betamethasone) or non-particulate (dexamethasone) corticosteroid, both of which are within current standards of care. Ultrasound or fluoroscopic guided injection will then be completed using sterile technique as per current clinic practice.

After the injection, patients will follow up in clinic or over the phone at 2 weeks, 3 months, and 6 months and will be asked their average NRS over the past week, functional questionnaires appropriate to pertinent body parts (WOMAC, ASES, QDASH), other treatments they have tried in the interim, and for any side effects they have experienced. In addition to obtaining outcome measures, the treating physicians may order repeat injections, medications, or refer the subject to surgery, at their discretion based upon the patient's pain and functional limitations. Up to a total of three injections to the same musculoskeletal structure are allowed during the 6 month study period. Any injection into a separate space (i.e. glenohumeral joint followed by subdeltoid bursa) will be considered different structures, and follow up for the new anatomical site will begin at the time of that injection. Data collection and follow up on the previous anatomical injection site will continue on the same timeline. Data on number and timing of repeat injections, surgeries, side effects, and medications will be recorded as part of the study.

Data analysis

Patients receiving injections to the intra-articular hip, glenohumeral joint, peri-tendinous biceps, and subdeltoid bursa will be analyzed separately. Depending on normality and cell counts, baseline measures between the particulate and non-particulate injection groups will be compared using two-sample t-tests or Mann-Whitney U-tests for continuous variables and chi-squared tests or Fisher's exact tests for categorical variables.

Within each joint/structure, a mixed-effects model will be used to compare differences in pain (NRS), function (WOMAC, ASES, QDASH), and the number of subsequent injections. These models will include adjustments for repeated measures and potential covariates as determined by the previous univariate tests. A power analysis determined that a sample size of 50 (25/group) will provide at least 80% power to detect 10% differences in pain and 25% differences in function between patients receiving particulate and non-particulate corticosteroids in the subdeltoid bursa and intra-articular hip, while a sample size of 36 (18/group) achieves the same power for patients receiving treatment in the glenohumeral joint, and a sample size of 62 (31/group) achieves this power in the biceps brachii group.

The time until a repeat injection was administered will be analyzed using a Cox proportional hazards survival model and chi-squared tests will be used to analyze repeat injections, repeat surgeries, and side effects between groups. All statistical analyses will be completed using a two-sided level of significance of 0.05.

Inclusion Criteria

- Age greater than or equal to 18
- Ability to provide informed consent
- Capable of complying with the outcome instruments used
- Capable of attending all planned follow up visits
- Patient is deemed appropriate for intra-articular hip, glenohumeral, peri-tendinous biceps, or subdeltoid bursa corticosteroid injection by their treating physician for the treatment of a painful musculoskeletal condition

-Average pain of greater than or equal to 4/10 over the last 7 days

Exclusion Criteria

- Unclear diagnosis
- Pregnancy
- Incarcerated patients
- Prior corticosteroid injection into the anatomical structure within the past 3 months
- Prior prosthetic surgery on the joint
- Any condition that increases injection risk such as bleeding tendencies, uncontrolled diabetes, current active infection, or infection requiring antibiotics within the last 7 days
- Chronic opioid use to control pain
- Workers compensation and litigation.
- BMI > 40

Data safety monitoring

Redcap will be used as a secure database in which to compile and capture all data. All data will be entered directly to the Redcap database. Data will be de- identified and coded through Redcap prior to exportation to spreadsheet form for data analysis. Devices that contain identifiable subject information will be password protected and encrypted. Access to the data will be limited exclusively to members of the research team until after de-identification. Thereafter, files may be shared electronically via encrypted, password protected email.

Participants will be asked to report all adverse events at the time of occurrence to the principal investigator, and information on minor side effects will be elicited via phone or appointment at 2 weeks, 3 months, and 6 months. As the procedures and medications used in this trial are current standard of care, we do not anticipate significant adverse events.

Procedure Plan

Time of Visit	Questionnaires	X-Ray or Ultrasound
Baseline	N/A	Standard care
Injection	Study	Standard care
2 weeks ($\pm 1w$)	Study	N/A
3months ($\pm 4w$)	Study	N/A
6 months ($\pm 4w$)	Study	N/A

9) Significance:

Currently there is no data to support the injection of one type of corticosteroid over another in the treatment of many musculoskeletal conditions. We hope that the results of this study will aide clinicians in selecting the most effective medication for musculoskeletal injections and resolve the clinical equipoise surrounding this question.

10) Key References

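### Section 5 predicts no significant difference, but the plan has no rule for reading p>0.05, so non-significant results could count as support without excluding a relevant difference

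*Combined protocol and SAP*

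**What the plan says.** Section 5 gives two aims and one hypothesis. The efficacy aim is a question of difference: "To determine if particulate or non-particulate corticosteroid injections are more effective at treating pain". The second aim asks in the same way whether the side effect profiles differ. The hypothesis is instead written as a forecast of test results: "There will be no significant difference in pain reduction, number of injections received, conversion to surgery, or side effect profile", at each of three follow-up times and for each of four structures.

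Section 8 (Data analysis) keeps the structures apart: "Patients receiving injections to the intra-articular hip, glenohumeral joint, peri-tendinous biceps, and subdeltoid bursa will be analyzed separately". Within each structure, "a mixed-effects model will be used to compare differences in pain (NRS), function (WOMAC, ASES, QDASH), and the number of subsequent injections". Time to a repeat injection goes to a Cox model, and "chi-squared tests will be used to analyze repeat injections, repeat surgeries, and side effects between groups". Every analysis is two-sided at 0.05.

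The sample sizes are 25 per group for the subdeltoid bursa and for the hip, 18 for the glenohumeral joint and 31 for the biceps. The plan says that these "will provide at least 80% power to detect 10% differences in pain and 25% differences in function".

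No section gives an equivalence or non-inferiority margin, a confidence-interval criterion, or a statement of how a non-significant result will be read.

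**The concern.** A test that fails to reject does not show that two treatments are alike; it may only show that there was too little information. A hypothesis of no significant difference is nevertheless supported by exactly that outcome, and smaller or noisier data support it more easily.

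The stake is the wording of the conclusion. Section 9 hopes that the results will guide the choice of drug and settle the present uncertainty. Section 6 gives, for epidural injections, a reason that a finding of no difference could feed: "dexamethasone is generally preferred due to comparable efficacy and improved safety profile of non-particulate steroids compared to particulate steroids". If the report followed section 5 as written, a structure with little information on surgery or side effects could be presented as bearing out the hypothesis.

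**Working it through.** **Inputs.** Group sizes n = 18 (glenohumeral), 25 (bursa; hip) and 31 (biceps), two-sided 0.05 and separate analysis by structure all come from section 8. The document gives no event rate, SD or margin. Steps 3 and 4 assume none of these. Triplets below are in the order 18 / 25 / 31 per group.

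**1. The plan's own figure.** The sample sizes cannot be reproduced, because no SD is given and the 10% is not said to be absolute or relative. They can only be inverted. At 80% power the standardized difference is (1.960 + 0.842) × √(2/n) = 0.93 / 0.79 / 0.71 (0.96 / 0.81 / 0.72 with the t distribution). This does not show the sizes to be wrong, and nothing below depends on it.

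**2. Hypothesis against analysis.**

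| Outcome in the hypothesis | Planned analysis | Stated power |
|---|---|---|
| Pain | mixed model | at least 80% for a 10% difference |
| Number of injections | mixed model; also chi-squared (repeat injection) and Cox (time to it) | none |
| Conversion to surgery | chi-squared | none |
| Side effects | chi-squared | none |

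One of the four outcomes has stated power. Function is powered but is not in the hypothesis.

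**3. Three events against none.** With k events against 0, the uncorrected Pearson statistic is 2kn/(2n − k), compared with 3.84.

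- k = 3: 108/33 = 3.27, 150/47 = 3.19, 186/59 = 3.15; p = 0.070 / 0.074 / 0.076. None is significant.
- k = 4: 144/32 = 4.50, 200/46 = 4.35, 248/58 = 4.28. Four is the first significant count against none.

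The Newcombe 95% interval for the risk difference combines the Wilson limits of the two arms. With 0 events in one arm, its upper limit is the Wilson upper limit of the other arm:

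[p + z²/2n + z√(p(1−p)/n + z²/4n²)] / (1 + z²/n), with p = 3/n and z = 1.960.

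The intervals are −4.0 to 39.2, −3.5 to 30.0 and −3.0 to 24.9 percentage points.

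**4. The least an interval can leave open.** With no events in either arm the interval is ± z²/(n + z²): 3.841/21.841 = 17.6, 3.841/28.841 = 13.3, 3.841/34.841 = 11.0 points. With one event in each arm it is ±20.7 / 15.9 / 13.2. Enumerating every pair of counts from 0 to n finds none whose interval lies within ±10 points at any of the three sizes. The 10 is an illustration, not a proposed margin.

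**5. Number of injections.** Section 8 says "Up to a total of three injections to the same musculoskeletal structure are allowed during the 6 month study period". A total between 1 and 3 cannot have an SD much above 1. The unadjusted half-width for a difference in means is t(0.975, 2n−2) × √(2/n) × SD = 0.68 / 0.57 / 0.51 SD. For an assumed SD of 0.5 to 1.0 this is 0.34–0.68 / 0.28–0.57 / 0.25–0.51 injections. The planned mixed model may do somewhat better or worse.

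**The case against.** **It is only a null hypothesis in an investigator's wording.** The aims ask about a difference, the tests look for one, and the power statement is for detecting one. This stands, and it limits the point. But the sentence forecasts non-significance. A null that is not rejected has not been confirmed, whereas a forecast of non-significance has come true. If a null was meant, saying so costs nothing.

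**One p>0.05 does not meet the hypothesis.** It covers four outcomes, three times and four structures together. Counting only one test per outcome per structure (16 tests), identical steroids would give at least one p<0.05 with probability 1 − 0.95^16 = 0.56, if the tests were independent (an assumption; correlation or sparse events would lower it). This stands too. Even if every test were non-significant, though, the intervals in steps 3 to 5 would be just as wide, and the separate analyses invite a reading structure by structure.

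**Wide intervals are a matter of sample size.** Correct: rewording narrows none of them. It changes what is said about them.

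**Pain is powered.** At 80% power the design difference D is 2.80 standard errors, so the 95% interval reaches D in one direction or the other when |Z| > 0.842, which has probability 0.40 if the steroids are identical. Among non-significant results (0.40 − 0.05)/0.95 = 37% therefore include D and 63% exclude it. This holds for any trial with 80% power, so I give it no weight against this one.

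**The epidural remark is drawn as a contrast** with the structures studied here. The chance that a no-difference report would be acted on is therefore an inference, not something the document states.

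A reader might go further and infer that this is an equivalence trial analysed with the wrong tests, or that its sample size should have been derived for equivalence. The document supports neither: no section undertakes to claim equivalence, and the 10% and 25% are differences to be detected, not margins.

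**Conclusion.** The point holds, confined to the section 5 hypothesis and the conclusion it permits. The design, tests and sample sizes can stand. As worded, non-significance at 18 to 31 per group would count in favour of the hypothesis, although at these sizes no possible result on surgery or side effects could exclude differences of 11.0 to 17.6 points in both directions.

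The binary figures need no assumed event rate; they rest on the planned sizes being reached with complete data, on the uncorrected chi-squared test and on Newcombe intervals. The figures for number of injections rest on an assumed SD. The point should be fixed before analysis, but it is no reason to redesign the trial.

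**What to change.** **Section 5.** Replace the forecast with the two-sided question that the aims ask. The null is no difference between particulate and non-particulate steroids; the alternative is a difference in either direction.

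**Section 8, Data analysis.** For each structure and outcome, report the between-group estimate with its 95% confidence interval: mean difference for pain, function and number of injections (from the planned mixed model), hazard ratio for time to repeat injection, and risk difference with a score-based interval for repeat injection, surgery and side effects. Add, for example: *A result with p>0.05 will not by itself be reported as similarity or as confirmation of no difference. It will be interpreted from the 95% confidence interval and described as inconclusive where that interval is wide.*

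**Cost.** Wording and reporting only, with no added patients, visits or tests. Some structures or outcomes, most likely surgery and side effects, will have to be reported as inconclusive.

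**Not part of this fix.** A formal claim of comparability would need its own prespecified, justified margin and its own power. The 10% should not become that margin by default, since its scale is not stated.

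**Separate point.** The hypothesis speaks of conversion to surgery and the analysis of repeat surgeries. The two should be reconciled to one defined outcome.

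### The plan does not assure a function score before the injection, and its covariate rule does not guarantee adjustment for any outcome's baseline score

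*Combined protocol and SAP*

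**What the plan says.** Three places in section 8 bear on this.

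- **Design, before randomisation.** The data collected are given as "After consenting, basic demographic data, average numeric pain score (NRS) over the past week, and information on other medical interventions tried for their pain". Randomisation and then the injection follow. No function instrument is listed.
- **Design, follow-up.** At 2 weeks, 3 months and 6 months patients are asked for NRS and "functional questionnaires appropriate to pertinent body parts (WOMAC, ASES, QDASH), other treatments they have tried in the interim", and about side effects. This is the only place in the Design text where the function scales are scheduled.
- **Procedure Plan table.** The first two rows read "Baseline N/A Standard care" and "Injection Study Standard care", where the middle entry is the questionnaire column. The three follow-up rows also carry Study in that column. The table names no instrument, and on the Injection row it does not say whether the questionnaires come before or after the injection.

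In Data analysis, within each structure, "a mixed-effects model will be used to compare differences in pain (NRS), function (WOMAC, ASES, QDASH), and the number of subsequent injections". Adjustment is for repeated measures and "potential covariates as determined by the previous univariate tests". The only univariate tests described before that point are the between-group comparisons of baseline measures. The same section states at least 80% power for a 25% difference in function and a 10% difference in pain, with 25, 18 or 31 patients per group depending on the structure.

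**The concern.** Function is a modelled outcome and appears in the power statement, yet nothing in the text secures its starting value. If a site follows the Design text literally, the first WOMAC, ASES or QDASH is taken two weeks after treatment. A score not taken before the injection cannot be recovered later. Change in function could then not be computed, and the model could not use the baseline score to reduce residual variance.

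The covariate rule adds a second gap, which reaches pain as well. A baseline score enters the model only if it happens to differ between arms in a significance test. That is unrelated to how well it predicts follow-up, which is what determines the gain from adjusting. The hypothesis is worded in terms of reduction in pain, but nothing guarantees that baseline NRS is in the pain model. With 18 to 31 patients per arm and four structures analysed separately, precision is scarce.

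**Working it through.** **1. The plan's own figure.** The stated sample sizes cannot be reproduced. The documents give no SD, no baseline/follow-up correlation, no dropout rate and no reference value for the percentages. The calculation can only be run backwards. With two-sided alpha 0.05 and 80% power, the detectable standardised difference is d = (1.960 + 0.842) × √(2/n):

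| n per group | Structure | d (normal) | d (t-test) |
|---|---|---|---|
| 25 | subdeltoid bursa, hip | 0.79 | 0.81 |
| 18 | glenohumeral | 0.93 | 0.96 |
| 31 | biceps | 0.71 | 0.72 |

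**2. What baseline adjustment is worth.** Let r be the correlation between baseline and follow-up score. The documents do not give it; I assume 0.3 to 0.7. Adjustment reduces the residual SD to SD × √(1 − r²), so the unadjusted variance is larger by a factor of 1/(1 − r²). The results below are for a single follow-up visit. They do not depend on n, because each d is set to give 80%.

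*Case A: the 80% refers to an unadjusted analysis.* Power after adjustment = Φ(2.802/√(1 − r²) − 1.960).

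| r | 1/(1 − r²) | 2.802/√(1 − r²) | Power |
|---|---|---|---|
| 0.3 | 1.10 | 2.937 | 83.6% |
| 0.5 | 1.33 | 3.235 | 89.9% |
| 0.7 | 1.96 | 3.923 | 97.5% |

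The second column means that adjustment is worth 10%, 33% or 96% more patients at the same enrolment.

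*Case B: the 80% already assumed baseline adjustment.* Power without it = Φ(2.802 × √(1 − r²) − 1.960), which is 76.2%, 67.9% or 51.6%. Restoring 80% would need n/(1 − r²) per group:

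| Planned n | r = 0.3 | r = 0.5 | r = 0.7 |
|---|---|---|---|
| 25 | 28 | 34 | 50 |
| 18 | 20 | 24 | 36 |
| 31 | 35 | 42 | 61 |

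The documents do not say which case applies.

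**3. What the covariate screen lets through.** A two-sided 0.05 t-test flags a baseline difference only when it exceeds t × √(2/n) in SD units:

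- n = 18: 2.032 × 0.333 = 0.68
- n = 25: 2.011 × 0.283 = 0.57
- n = 31: 2.000 × 0.254 = 0.51

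At r = 0.5, an imbalance just below these limits moves the unadjusted follow-up difference in that sample by half as much: about 0.34, 0.28 or 0.25 SD. The detectable differences are 0.96, 0.81 and 0.72 SD. This is not a bias and not an additional loss. It is the same chance variation that the standard error in step 2 already contains, and it shows that the screen does little to remove it.

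**The case against.** A reader might infer that function is definitely first measured after the injection, so that baseline adjustment is impossible and the trial is underpowered. The documents do not support that.

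- **The Injection row.** It schedules study questionnaires with the same entry as the follow-up visits, where the function scales are given. If they include those scales and are completed before the injection, a starting value exists. The text leaves this open; it does not rule it out.
- **The Baseline row.** Its N/A looks like a contradiction of the NRS collection, but it need not be. Patients choose the injection before the study is mentioned, so Baseline may be the routine visit before consent, with consent, NRS, randomisation and injection all falling under the Injection row. On that reading, simply changing the Baseline entry to Study could place questionnaires before consent.
- **Power.** No shortfall against 80% is shown. Case A is a possible gain above 80%, and Case B holds only if the planners assumed adjustment, which they do not say. Baseline NRS might also absorb part of the variance in function if it were in the model.
- **Validity and stakes.** Under randomisation the unadjusted follow-up comparison is unbiased, and its standard error allows for chance imbalance. The aims and hypothesis in section 5 do not name function, and baseline NRS is collected.

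All of this stands, and it limits the point to assurance and precision. It does not remove it. No sentence commits the trial to a pre-injection function score, and the only description of pre-randomisation data omits one. The stated rule does not guarantee use of baseline NRS. Adjusting for repeated measures does not settle this either, because the plan does not say whether the baseline value is among the repeated measurements.

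**Conclusion.** The point holds as a gap in specification with a cost in precision. A pre-injection WOMAC, ASES or QDASH is not assured, and no outcome's baseline score, including NRS, is guaranteed a place in its model. If the stated 80% is for an unadjusted analysis, adjustment would bring it to about 84%, 90% or 97.5% at r = 0.3, 0.5 or 0.7. These figures rest on assumed correlations, a single follow-up visit and a normal approximation. The direction is firm; the size cannot be fixed from the documents. The comparison without adjustment remains valid. The change is well worth making, because it is cheap and a missed baseline cannot be recovered, but the gap does not threaten the trial's stated aims.

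**What to change.** 1. In Design, state that NRS and the function scale appropriate to the injected structure are completed after consent and before randomisation and injection.
2. In the Procedure Plan table, reconcile the Baseline and Injection rows with that text: define each visit relative to consent, name the instruments, and state that they precede the injection. No study questionnaire should fall before consent.
3. In Data analysis, include the baseline score of each pain and function outcome as a prespecified fixed covariate in its mixed model, whatever the baseline tests show.
4. State whether the 80% power assumes this adjustment and, if so, the correlation used.

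The cost is a few minutes of questionnaires at a visit that already takes place, plus the wording changes. No additional visit or patients are needed.

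### Does a later injection into a different structure bring non-randomised records into that structure's particulate versus non-particulate comparison?

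*Combined protocol and SAP*

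**What the plan says.** All of this is in section 8 of the combined protocol and SAP.

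- **Randomisation (Design).** After consent and baseline data: "The participant will then be randomized to receive either a particulate (triamcinolone or betamethasone) or non-particulate (dexamethasone) corticosteroid". No second randomisation is described.
- **Further treatment (Design).** Treating physicians may order repeat injections, medication or surgical referral "at their discretion based upon the patient's pain and functional limitations".
- **Status of a new site (Design).** "Any injection into a separate space (i.e. glenohumeral joint followed by subdeltoid bursa) will be considered different structures".
- **Timing at a new site (Design).** The clock restarts there: "follow up for the new anatomical site will begin at the time of that injection". The first site is not dropped: "Data collection and follow up on the previous anatomical injection site will continue on the same timeline".
- **Analysis (Data analysis).** "Patients receiving injections to the intra-articular hip, glenohumeral joint, peri-tendinous biceps, and subdeltoid bursa will be analyzed separately". Pain, function and number of later injections are compared in a mixed-effects model for each structure.
- **Targets (Data analysis).** 50 (25 per group) for bursa and for hip, 36 (18 per group) for glenohumeral joint, 62 (31 per group) for biceps. Power is described "between patients receiving particulate and non-particulate corticosteroids in the subdeltoid bursa and intra-articular hip", with similar wording for the other two.

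The three-month exclusion for a previous steroid injection applies to the structure in question. A recent glenohumeral injection therefore does not by itself bar a bursa record.

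**The concern.** One participant can supply data on two structures, and the second set begins after treatment of the first. The second injection may be ordered because the first did poorly. If its class were then picked by the physician, its record would be an observational comparison inside a randomised trial. Even with the participant's allocated class kept, who reaches the second structure could depend on how the first drug worked, and that drug might still be acting.

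The groups are small, so a few such records could count: one record is 1/50 = 2.0%, 1/36 = 2.8% or 1/62 = 1.6% of a target. The analysis and power sentences speak of patients receiving injections, not of injections randomised for the structure. Read literally, that would let the later records in.

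**Working it through.** **What the text settles.** The sentence on the new site is a rule for data collection. The sentence on separate analysis says the four structures are not pooled. The power sentence names the two arms. None of them says that a later-site record joins the new structure's comparison. Entry is an inference, though a fair one, because nothing excludes it. The structures are modelled separately, so a participant who contributes to two of them does not create dependence between participants within one model.

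**Three possible readings of the later injection's class**

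1. *Freshly randomised.* No bias from this source.
2. *Carried over from the participant's allocation.* Class is still random. Selection after treatment and possible persistence of the first drug remain.
3. *Picked by the physician.* Not randomised.

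**Scale, taken from the plan's own figures.** The plan gives no SD, so its sample sizes cannot be reproduced directly. Assume that the 10% pain difference is 1 NRS point. Then 80% power at two-sided 0.05 with 25 per group implies

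SD = 1 / [(1.960 + 0.842) × √(2/25)] = 1 / (2.802 × 0.2828) = 1.26, and SE = 1.26 × 0.2828 = 0.357.

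The SE is the same for 18 and 31 per group, because it equals 1/2.802 whenever power is set at 80% for 1 point.

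**Reading 3.** Let f be the share of non-randomised records and b the prognostic difference between classes within them (both assumed). Bias = f × b, d = f × b / 0.357, and the false-positive rate is Φ(d − 1.96) + Φ(−d − 1.96).

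| f | b = 0.5 point | b = 1 point |
|---|---|---|
| 10% | 5.2% | 5.9% |
| 20% | 5.9% | 8.7% |
| 30% | 7.1% | 13.4% |

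**Reading 2.** Work in SD units with 25 per group. Assume that later records come from the worst 20% of first-site responders, that the correlation between sites is 0.5, and that no effect of the first drug persists.

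- *Classes equal at the first site.* Both classes send the same 20%, each with mean deviation 1.400. The difference is 0 and the false-positive rate stays at 5%.
- *Classes differ by 0.8 SD at the first site.* The cut-off c solves ½[1 − Φ(c − 0.4)] + ½[1 − Φ(c + 0.4)] = 0.20, so c = 0.910. The less effective class sends 30.5% of its patients and the other 9.5%. Their mean deviations from their own class mean are φ(0.510)/0.305 = 1.149 and φ(1.310)/0.095 = 1.779. Multiplied by 0.5, these become 0.574 and 0.889 at the second site.
 - Equal later share in each arm: bias = f × (0.889 − 0.574) = f × 0.315, which is 0.032 SD at f = 10% and 0.063 SD at 20%.
 - Direct enrolees split equally, later records in the ratio 30.5 to 9.5: at 10%, (3.81/26.31) × 0.574 − (1.19/23.69) × 0.889 = 0.039 SD. At 20%, (7.62/27.62) × 0.574 − (2.38/22.38) × 0.889 = 0.064 SD. The sign is opposite to the previous case.
 - False-positive rate: with SE = √(2/25) = 0.283 SD, d runs from 0.032/0.283 = 0.11 to 0.064/0.283 = 0.23, giving 5.1% to 5.6%.

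**Cost of leaving such records out.** If they had counted towards the targets, power would fall from 80% to Φ(2.802 × √0.9 − 1.96) = 75.7% at an assumed 10%, and to Φ(2.802 × √0.8 − 1.96) = 70.7% at 20%. Nothing is lost if targets are counted in randomised injections.

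**The case for a change.** The best case for a change is that the text leaves three readings open, so two analysts could build different analysis sets from the same data, and a few sentences would settle it before outcomes are seen. That a participant keeps one class throughout is itself unwritten, and it would still leave selection after treatment. A new follow-up clock, treatment as a different structure, and analysis described by receipt of an injection all point towards inclusion.

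Most of this is correct as description. The plan is silent, and persistence of the first drug could add to the bias worked out above by an amount that the documents do not allow anyone to estimate. What does not stand is the step from silence to a defect. Receiving is weak evidence of an as-treated population in a design that section 8 calls a randomised controlled trial. The sentence on physicians' discretion concerns repeat injections, and its extension to a new structure is plausible but not stated. Treating a carried-over class like a chosen one overstates the threat, since only the decision to inject is then non-random. Reporting carried-over records descriptively, or keeping them and checking the result without them, is a matter of preference.

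**Conclusion.** No change to the plan follows. This is a missing detail that analysts can fill sensibly. The allocation record shows whether a later injection's class was randomised. A record with a chosen class has no place in a randomised comparison, and records with a carried-over class can be checked by running the model with and without them. Participants enrolled directly for a structure keep the protection of randomisation under every reading.

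The size of any effect is undetermined, because the documents give neither the frequency of later-structure injections nor the class rule for them. It is nil under fresh randomisation. Selection under a carried-over class gives no bias if the classes do not differ, which is the trial's stated hypothesis. With an assumed 0.8 SD first-site difference it is about 0.03 to 0.06 SD, of either sign. The larger false-positive rates, up to 13.4%, need a physician-chosen class, 30% of records and a 1-point imbalance together, none of which the plan states. These figures rest on 25 per group, the assumed shares and correlation, and no persisting effect of the first drug.
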